8.1 Adverse events

Ocular and systemic safety and tolerability of a single IVT injection of UBX1325 will be evaluated by treatment-emergent adverse events (TEAEs). A TEAE is an adverse event that occurs after the initiation of the study treatment (*i.e.*, the onset date is the same as or after Day 1), or an adverse event with onset prior to the study treatment that worsens in severity or becomes serious after the initiation of the study treatment. Summary tables will include only TEAEs, and listings will include all adverse events reported in the clinical database.

The following summaries of TEAE data will be performed by study arm and overall:

- Overall summary of TEAEs
- TEAEs by SOC, PT, and severity
- Ocular TEAEs in the study eye by PT
- Treatment-related ocular TEAEs in the study eye by PT, severity
- Treatment-emergent serious adverse events by PT

Overall summary of TEAEs will include the number and percentage of patients experiencing at least one TEAE, related TEAE, grade >=3 TEAE, serious TEAE, and TEAE leading to death.

For summaries by SOC and PT, a patient will only be counted once for each PT and once for the overall count for a SOC. However, patients may be included in more than one PT category within a SOC. For summaries which also include severity, a patient who experiences the same event more than once will have the event with the worst severity counted in the summary. Summaries by SOC and PT will be presented by SOC alphabetically then by descending frequency of PT within SOC based on the overall column.

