5.1.9 Ocular Evaluations (must be conducted on both eyes)

- BCVA: should be assessed using the ETDRS chart starting at 4 meters at Screening, on Day 1 (pre-dose), Day 2, and at Weeks 1, 2, 4, 8, 12, 18, 24, 32 and 48, and Unscheduled/ET. See the Ophthalmic Manual for details.
- Anterior Segment Evaluation: should be performed prior to pupillary dilation, or after, depending on the site Standard of Care. Any abnormalities of the anterior chamber, eyelids, conjunctivae, pupil, iris, lens and cornea should be documented at Screening, on Day 1 pre-dose and post-dose, on Day 2, and at Weeks 1, 2, 4, 8, 12, 24, 32 and 48 and Unscheduled/ET. Any anterior chamber inflammation (cells and flare), phakic status, and posterior lens capsule status should also be noted. For post-dose, only the study eye should be assessed
- Posterior Segment Evaluation/Ophthalmoscope Examination: should be performed after pupillary dilation to examine the vitreous body, optic nerve head, macula, posterior pole, and peripheral retina at Screening, on Day 1 pre-dose and post-dose, on Day 2, and at

Weeks 1, 2, 4, 8, 12, 24, 32 and 48/ET. Any vitreous inflammation (haze and cells) should also be noted. For post-dose, only the study eye should be assessed

- IOP: should be measured using Goldmann applanation tonometry at Screening, on Day 1 pre-dose and 30 minutes ± 15 minutes post-dose, on Day 2, and at Weeks 1, 2, 4, 8, 12, 24, 32 and 48 and Unscheduled/ET. Tonometry should be performed prior to pupillary dilation or as per site's standard procedures. For post-dose, only the study eye should be assessed
- CFP: should be obtained at Screening, Visit 9 (Week 24), Visit 12 (Week 48) and Unscheduled/ET.
- FA: should be obtained at Screening (or on Day 1 pre-dose) and at Weeks 4, 12, 24 and 48, and Unscheduled/ET (if it had not been done within 30 days prior).
- SD-OCT: should be obtained at Screening, on Day 1 (pre-dose), and at Weeks 1, 2, 4,8, 12, 18, 24, 32, 40 and 48 and Unscheduled/ET.
- OCT-A: to be conducted at sites with the proper equipment available at Screening, Weeks 12, 24 and 48 and Unscheduled/ET.

CFP, FA, SD-OCT, and OCT-A (if done) images should be transmitted to the Central Reading Center at each applicable visit.

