2.1 Trial design

This is a Phase 2a, prospective, randomized, double-masked sham-controlled two-arm clinical trial. Patients will be randomized in a 1:1 ratio to UBX1325 or sham arm, stratified by most recent anti-VEGF treatment that patients received prior to Day 1. There will be two strata: 1) aflibercept vs 2) ranibizumab or bevacizumab. Each patient will be administered a single 50 μ L UBX1325 IVT injection or sham procedure on Day 1 and be followed for up to 54 weeks (6-week screening period + 1 dose day + 24-week follow-up period + 24-week extended follow-up period). This is a multicenter trial that plans to enroll patients at approximately 32 sites in the U.S. and Canada. A study schematic is shown below (Figure 1 from the study protocol). Schedule of visits and assessments is presented in Appendix A.

Figure 1 Schematic of Phase 2a Proof-of-Concept Study

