2.4 Determination of sample size

Assuming the difference of change from Baseline in BCVA between UBX1325 and sham is 8 letters, the standard deviation is 13 letters, and the drop-out rate is 5%, a sample size of 62 subjects (31 per group) would provide 80% power to detect the difference at a two-sided significance level of 0.15.

3. General Methods

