7.1 Secondary endpoints

The following continuous secondary efficacy endpoints will be analyzed using mixed models for repeated measures (MMRM):

- Change in BCVA from Baseline to Weeks 12, 24, and 48
- Change in CST from Baseline to each study visit as assessed by SD-OCT and read by a Reading Center
- Area under the curve (AUC) of change from baseline of CST for each study visit
- Area under the curve (AUC) of change from baseline of BCVA for each study visit

The MMRM will be used for the primary analysis of the change from baseline in BCVA, which is based on the ETDRS VA chart assessed at a starting distance of four meters. The model will include the change from baseline at Day 2, Week 1 to Week 48 as the dependent variable, and the independent variables will include continuous BCVA baseline, categorical treatment arm

(active or sham), categorical study visit, and arm-by-visit interaction. Within-subject correlation will be modeled using subject-specific random intercepts. The model will assume a compound symmetry covariance structure. If there are convergence problems with this model, then other covariance structure may be fitted. The primary analysis will be limited to data collected prior to or on the rescue date. A supportive analysis will be performed for all data collected, regardless of rescue therapy. Subjects who violated major inclusion or exclusion criteria will be excluded from the primary and supportive analyses.

When BCVA outliers occur, a sensitivity analysis excluding the outliers will be performed. If deemed appropriate, other sensitivity analyses may also be considered to assess the impact of outliers.

The change from baseline in CST, as assessed by SD-OCT and read by a Reading Center, AUC of change from baseline in BCVA and CST, will be analyzed using MMRM, same as the analysis of BCVA.

The following binary secondary efficacy endpoints will be summarized:

- Proportion of patients who require 2 or more, or 1 or more anti-VEGF rescue over 12, 24, and 48 Weeks
- Proportion of patients without macular fluid at Weeks 12, 24, and 48 as assessed by SD-OCT

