Proportion of patients who require 2 or more, or 1 or more anti-VEGF rescue over 12, 24, and 48 Weeks will be summarized for each treatment group. Confidence intervals of difference in proportions between treatment groups will be calculated using an exact method (Chan and Zhang, 1999) implemented in the SAS procedure Freq. Criteria for rescue therapy are worsening of CST by 75 μ m relative to Baseline and/or a 10-letter decrease in BCVA compared to peak BCVA from Baseline. Patients who meet rescue criteria can be rescued with anti-VEGF treatment. Rescued patients will continue with study visits per protocol. Proportion of patients without macular fluid at Weeks 12, 24, and 48 as assessed by SD-OCT will be analyzed using same method.

BCVA and SD-OCT data will be listed.

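### SAP Section 8 does not summarise measured vision loss or intraocular inflammation: both reach the safety tables only if an investigator reports them as adverse events

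*SAP*

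**What the plan says.** SAP 1.2.1 makes local and systemic safety and tolerability the primary objective. SAP 8.1 gives the basis of assessment: "Ocular and systemic safety and tolerability of a single IVT injection of UBX1325 will be evaluated by treatment-emergent adverse events (TEAEs". The rest of SAP Section 8 covers IOP, laboratory data, ECG, vital signs and physical examination.

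The ocular data collected are wider than that. Protocol Table 1 schedules BCVA at all 11 post-dose visits, and both segment examinations at every one except Week 18. (Protocol 5.1.9 leaves out Week 40 for BCVA and the segment examinations, so the two lists should be reconciled.) Protocol 5.1.9 asks for anterior chamber cells and flare to be recorded, and for the posterior segment says "Any vitreous inflammation (haze and cells) should also be noted".

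BCVA is analysed in SAP 7.1 as efficacy. One limb of the rescue criterion is "a 10-letter decrease in BCVA compared to peak BCVA from Baseline". Protocol 5.1.10 applies it from Week 2 onward or at an unscheduled visit, makes rescue optional, and does not ask for a cause. Rescue counts are a secondary efficacy endpoint. For the BCVA model, "The primary analysis will be limited to data collected prior to or on the rescue date". A supportive model uses all data regardless of rescue.

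**The concern.** BCVA and the segment examinations are the most direct measures of ocular harm after an intravitreal injection. In this plan they become safety results only when someone decides that a finding is an adverse event. No letter-loss or inflammation threshold triggers an AE report (Protocol 7.2.2), and no events of special interest are defined (Protocol 7.4). In DME a fall in vision can readily be put down to the underlying disease, and Protocol 7.1 grades an event most likely explained by the patient's clinical state as unlikely related.

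Meanwhile the same fall can qualify the eye for rescue, be counted as an efficacy outcome, and end that eye's contribution to the primary BCVA model after the rescue date. The summaries that remain compare means, which are a poor way to see a few severe losses in a small arm. What is at stake is whether a reader of the primary safety results can compare the arms on measured vision loss and inflammation.

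**Working it through.** **1. What is measured against what is summarised as safety.**

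| Measurement | Post-dose visits in Protocol Table 1 | Summary in SAP Section 8 |
|---|---|---|
| IOP | 10 of 11 | By visit, plus counts at any post-baseline visit: at least 25, 30, 35 mmHg; rise of at least 10, 20 mmHg (8.2) |
| Hematology and chemistry | Weeks 24, 48 | Values, changes, shift tables (8.3) |
| BCVA | 11 of 11 | None from the measurement |
| Anterior and posterior segment findings | 10 of 11 | None from the measurement |

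The SAP therefore already accepts, for IOP and laboratory data, that measured values are summarised without waiting for an AE report.

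**2. The plan's own figure.** SAP 2.4: "Assuming the difference of change from Baseline in BCVA between UBX1325 and sham is 8 letters, the standard deviation is 13 letters"; "the drop-out rate is 5%, a sample size of 62 subjects (31 per group"); "80% power to detect the difference at a two-sided significance level of 0.15". SAP 2.1: "randomized in a 1:1 ratio to UBX1325 or sham arm". Normal approximation: n per arm = 2 × (1.4395 + 0.8416)² × (13/8)² = 27.5, so 28; 28/0.95 gives 30 per arm, N = 60. With the noncentral t, 29 per arm are needed; 29/0.95 gives 31 per arm, N = 62. The stated size reproduces. It matters here only because it fixes 31 treated eyes and an SD of 13.

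**3. What a mean shows.** Assume, purely for illustration, that two treated eyes each lose 20 letters.
- Share of eyes: 2/31 = 6.5% (exact 95% interval 0.8% to 21.4%).
- Shift in the arm mean: 2 × 20/31 = 1.29 letters.
- Standard error of a simple arm difference with the plan's SD: 13 × √(2/31) = 3.3 letters.

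The shift is about 0.4 of a standard error (1.29/3.3), so the mean would not show it. A count would.

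**4. How few events to expect.** The chance of at least one case among 31 is 1 − 0.98³¹ = 47% at a true rate of 2%, and 1 − 0.95³¹ = 80% at 5%. Zero cases in 31 leaves a one-sided 95% upper limit of 9.2%. These figures hold whichever tables are planned and do not show that any event would be misfiled. They show only that each event carries weight.

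**5. Effect of the rescue-date cut.** Simulation on assumed inputs: 10% or 20% of the active arm loses 15 letters permanently from Week 8; between-patient SD 8; within-patient SD 3 or 4; every eye meeting the BCVA limb is rescued; rescue does not change BCVA; random-intercept model with known variances, 3,000 per arm. Arm differences in letters:

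| Share affected, within-SD | True, from Week 8 | SAP rule, Week 8 | SAP rule, Week 12 | SAP rule, Week 48 | All data, Week 48 |
|---|---|---|---|---|---|
| 10%, 3 | −1.5 | −1.58 | −0.20 | −0.23 | −1.39 |
| 10%, 4 | −1.5 | −1.67 | −0.48 | −0.11 | −1.47 |
| 20%, 3 | −3.0 | −3.18 | −0.76 | −0.73 | −3.14 |
| 20%, 4 | −3.0 | −2.86 | −0.55 | +0.02 | −2.76 |

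The loss shows in full at Week 8, where it begins, because the rescue-date value is kept. It is then largely lost from later visits. These inputs also rescue 42% to 73% of unaffected eyes, so the table shows direction and not expected size.

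**6. Why the all-data model does not close the gap.** It recovers the mean difference, but it is still a comparison of means. SAP 7.1 excludes major eligibility violators from it, so it is not a Safety Analysis Set result. SAP 3.3 and Appendix B keep one visit per window, normally the one nearest the planned day, so an unscheduled visit for acute vision loss can be passed over.

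**The case against.** Two stronger readings are tempting, and the documents support neither.

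A reader might infer that drug-related vision loss or inflammation appears in no safety table, or only as an efficacy result. That is not so. Protocol 7.1 defines an AE as any untoward occurrence, related or not. Protocol Section 7 requires assessment for signs of toxicity at each visit. Anything reported enters the SAP 8.1 tables of ocular study-eye events. Protocol 2.3.5.1 shows that even disease progression was recorded as a study-eye AE in eight Phase 1 patients. Nothing suggests that toxic losses would go unreported. The defect is that the tables depend on that step.

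A reader might also infer that a toxic 10-letter loss is removed from the primary BCVA model. It is not: the rescue-date value stays, and only later visits go. Rescue is also optional, and the scheduled Day 2 and Week 1 visits fall before its window. A single rescue counts only in the summary of one or more rescues, not in the defined endpoint of two or more.

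Three further points have weight. BCVA is listed by patient, so each severe loss among 31 treated eyes can be found. Table specifications are in a separate document (SAP Section 1), which may contain more. The safety committee may review all acquired data. But listings give no comparison by arm, and the SAP is where safety summaries should be prespecified. Finally, the protocol states no grading scale for cells, flare or haze, so a table by grade cannot be assumed feasible. The fix allows for this.

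**Conclusion.** The point holds as a gap in the safety summaries. Measured BCVA loss and segment-examination inflammation reach SAP Section 8 only through AE reporting, and no planned efficacy analysis replaces a by-arm count. The illustrated size is 6.5% of treated eyes against 1.3 letters in the arm mean. It rests on an assumed two eyes losing 20 letters, which is not a figure from the documents. The dilution after rescue likewise rests on simulated inputs. The gap itself needs neither; it follows from comparing Protocol Table 1 and 5.1.9 with SAP Section 8. The change should be made because it is cheap and bears on the primary objective. It does not invalidate the efficacy analysis or show that harm would be hidden.

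**What to change.** Add to SAP Section 8, on the Safety Analysis Set and by arm:

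- The number and percentage of study eyes with BCVA loss of at least 10, 15 and 30 letters from Day 1 at any post-baseline visit, also split before and after first rescue, with the fellow eye alongside.
- The number and percentage of study eyes with new or worsened anterior chamber cells or flare, or vitreous cells or haze, against baseline. Report by presence, or by worst grade where a grade was recorded.

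Both should use all observed visits, including unscheduled and post-rescue visits. The text should exempt them from the one-visit-per-window rule, which SAP 3.3 otherwise applies to all ocular data.

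The cost is two or three descriptive tables from data the protocol already requires. Some losses in either arm will reflect DME progression, so the counts must be read against sham. The rescue rule, sample size and efficacy models stay as they are.

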5.1.10 Rescue Criteria

If at any visit between Visit 4 (Week 2) to Visit 12 (Week 48) or Unscheduled, patients exhibit worsening CST by 75 µm from Baseline (Day 1) per SD-OCT and/or a 10-letter decrease in BCVA compared to peak BCVA from Baseline (Day 1), they can be rescued with standard of care. For this study, standard of care is defined as the last anti-VEGF a patient was administered prior to enrolling into the study. Rescued patients will continue their visit schedule as safety follow-up through Week 48. For any questions on rescue criteria, and prior to administering rescue medication, when possible, please contact the Medical Monitor or designee. Rescued patients continue with study visits per protocol. If additional visits are required outside of study visit windows, these will be considered unscheduled visits.

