6.5 Administration of Sham Procedure

Control will be a sham procedure (i.e., needleless, empty sterile syringe) touched to the surface of the study eye to mimic an IVT injection. Please refer to the current Pharmacy Manual for details on how to prepare and administer the sham procedure.

Patients may be prescribed prophylactic antibiotic eye drops following a sham procedure per the site's preferred practice patterns. Such drops, if prescribed, should be documented in the patient's eCRF.

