7.2 Documenting Adverse Events

7.2.1 Timeframe for Collection

AEs and SAEs will be collected from the time of treatment through the last follow-up visit at Week 48. All events prior to this will be documented as medical history.

The Investigator must follow up on all AEs through Week 48. Non-serious AEs may be followed to resolution past the patient's last study visit at the discretion of the Investigator and/or MedicalMonitor if in the best interest of the patient and the assessment of safety of UBX1325. The Investigator must follow up on all SAEs until the events have subsided, returned to Baseline, or,in case of permanent impairment, the condition stabilizes.

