1.2. Study objectives

1.2.1 Primary objective

• Assess local and systemic safety and tolerability of UBX1325 following a single-dose IVT injection compared to sham procedure in patients with DME

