1.3 Study endpoints

1.3.1 Primary endpoint

• Ocular and systemic safety and tolerability of a single IVT injection of UBX1325 evaluated by treatment emergent adverse events (TEAEs)

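### SAP 8.1 does not separate adverse events before and after rescue injections, so an ocular excess from the UBX1325 injection may be diluted if sham patients are rescued more often

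*SAP*

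**What the plan says.** The primary objective in SAP 1.2.1 is comparative: "Assess local and systemic safety and tolerability of UBX1325 following a single-dose IVT injection compared to sham procedure in patients with DME". The endpoint is treatment-emergent adverse events (TEAEs). SAP 8.1 defines them by a start only: "A TEAE is an adverse event that occurs after the initiation of the study treatment". Protocol 7.2.1 sets the end: "AEs and SAEs will be collected from the time of treatment through the last follow-up visit at Week 48". On the tables, SAP 8.1 says: "The following summaries of TEAE data will be performed by study arm and overall". Under SAP 4 the arms are formed by treatment actually received.

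On exposure to needles, Protocol 6.5 says: "Control will be a sham procedure (i.e., needleless, empty sterile syringe) touched to the surface of the study eye". Under Protocol 5.1.10, patients whose CST or BCVA worsens past a threshold at a scheduled visit from Week 2 on, or at an unscheduled visit, are eligible for rescue: "they can be rescued with standard of care". Standard of care there means the patient's last anti-VEGF before enrolment. Inclusion criterion 2 (Protocol 4.5) lists the agents, all given intravitreally, and Protocol 6.8.2 makes rescue the only DME treatment allowed in the study eye. Rescued patients stay in safety follow-up to Week 48. Repeat rescue is foreseen, since needing two or more rescues is a secondary endpoint.

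SAP 7.1 does deal with rescue for efficacy. The main BCVA analysis stops at the rescue date, and a supportive analysis uses all data. SAP 8.1 has no counterpart.

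**The concern.** A UBX1325 patient has one needle entry on Day 1 and a sham patient has none. Protocol 6.4 names complications of the injection itself, such as vitreous haemorrhage and retinal tears. Any ocular excess from the UBX1325 injection, whether due to drug or procedure, should show up in the contrast with the needleless sham.

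Rescue narrows that contrast. It is the only needle entry into the study eye that the protocol provides for sham patients, and events that follow it are counted as TEAEs of the sham arm. If sham patients are rescued more often, the sham rate rises more than the UBX1325 rate and the difference shrinks. A reader of the 48-week tables could not tell whether similar ocular event rates mean that UBX1325 adds little or that rescue injections filled in the sham arm.

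**Working it through.** **The plan's own figure.** The only calculated figure is the sample size (SAP 2.4): 8 letters, SD 13, two-sided 0.15, 80% power, 5% drop-out. The normal formula gives n = 2 × (1.440 + 0.842)² × 13² / 8² = 27.5, so 28 per arm; 28/0.95 rounds up to 30 per arm, or 60 in total. With the noncentral t, 28 per arm gives 79.99% power, so 29 are needed; 29/0.95 = 30.5, so 31 per arm, or 62. The figure is sound and this point does not affect it. No figure is given for TEAEs.

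**Does the plan imply unequal rescue?** Take the sponsor's 8 letters and SD 13, and assume normal changes with a sham mean of 0. A loss of 10 letters from baseline at one visit then has probability Φ(−10/13) = 22.1% in sham and Φ(−18/13) = 8.3% in UBX1325. For sham means from −4 to +4 the pairs run from 32%/14% to 14%/5%. These are not rescue rates: they leave out the CST criterion, loss measured from peak, repeated visits and the investigator's discretion. They show only the direction.

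**Model for the size.** Everything here is assumed:
- b: background risk of an ocular study-eye TEAE to Week 48, 20% in both arms
- q: risk of such an event per real injection, 5%, 10% or 20%
- r: share of the arm rescued
- k: injections per rescued patient, 1 or 3
- injections act independently of each other and of background risk

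With h = 1 − (1 − q)^k:
- Sham: P = 1 − (1 − b)(1 − r·h)
- UBX1325: P = 1 − (1 − b)(1 − q)(1 − r·h)
- Difference due to the Day 1 injection alone: (1 − b)·q

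Worked case, q = 10%, k = 3, rescue 50% sham and 30% UBX1325:
- h = 1 − 0.9³ = 0.271
- Sham: 1 − 0.8 × (1 − 0.5 × 0.271) = 30.8%
- UBX1325: 1 − 0.72 × (1 − 0.3 × 0.271) = 33.9%
- Difference +3.0 points, against 0.8 × 10% = +8.0 without rescue

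With 31 per arm, that is 10.5 against 9.6 patients with an event, instead of 8.7 against 6.2.

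Difference UBX1325 minus sham in points, by share rescued (sham/UBX1325):

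| q | k | Day 1 injection alone | 30%/30% | 50%/30% | 60%/20% |
|---|---|---|---|---|---|
| 5% | 1 | +4.0 | +3.9 | +3.1 | +2.4 |
| 5% | 3 | +4.0 | +3.8 | +1.5 | −0.7 |
| 10% | 1 | +8.0 | +7.8 | +6.2 | +4.6 |
| 10% | 3 | +8.0 | +7.3 | +3.0 | −1.1 |
| 20% | 1 | +16.0 | +15.0 | +11.8 | +9.0 |
| 20% | 3 | +16.0 | +13.7 | +5.8 | −1.2 |

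With equal rescue the shift is (1 − b)·q·r·h. At r = 30% and k = 3 that is 0.2 points for q = 5% and 0.65 for q = 10%. For q = 10% and k = 3 it passes 1 point only above r = 0.01/(0.08 × 0.271) = 46%.

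If the 22.1% and 8.3% above are used as rescue shares (q = 10%, k = 3), sham is 24.8% and UBX1325 29.6%, so +8.0 becomes +4.8.

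**Would patient-time rates help?** Suppose both arms carry the same 5% risk, all of it early, and mean pre-rescue time is 40 weeks on UBX1325 and 20 weeks on sham. The rates are 0.05/(40/52) = 0.065 and 0.05/(20/52) = 0.13 per patient-year: a false sham excess where the risks are equal. Rates per patient-time mislead when events cluster at an injection.

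**The case against.** **The summary is descriptive and legitimate.** Protocol 8.6 plans descriptive safety summaries and SAP 8.1 has no test. Counting every event by arm to Week 48 is a valid treatment-policy summary. The Protocol 3 version of the primary objective does not mention sham, although the synopsis and SAP 1.2.1 do. This stands: the full tables should stay, and at 31 per arm a 5-point difference is about 1.5 patients. But the plan does not name that estimand, and it does not isolate the effect of a single UBX1325 injection.

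**Early events can already be seen.** The post-dose, Day 2 and Week 1 examinations come before the first scheduled rescue opportunity at Week 2, and SAP 3.4 plans analyses at 12 and 24 weeks as well as 48. This helps with acute complications. It does not give a pre-rescue table, because the Week 12 cut already mixes in rescue.

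**The treatment-related table separates causes.** Protocol 7.1 sends events with another cause, such as concomitant medication, to the unlikely or unrelated grades. This helps in part. Relatedness is graded only to Study Drug, which Protocol 6.1 defines as UBX1325 in solution. There is no grade for the injection procedure or for rescue, and graders after Day 1 are masked.

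**The stronger reading.** A reader might infer that the primary comparison is confounded and biased towards UBX1325 looking as safe as sham, even to a reversed sign, and that the comparison should rest on pre-rescue data. The documents do not support this. They give no rescue rate, no number of injections and no event risk per injection. With no background events and q = 5%, a reversal to 9.8% against 14.3% requires every patient in both arms to be rescued, once on UBX1325 and three times on sham. Nor is the pre-rescue period a clean comparison: rescue is triggered by worsening that may itself be harm, and Protocol 2.3.5.1 reports disease progression as a study-eye adverse event in 8 Phase 1 patients.

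**Conclusion.** The point holds as a gap in presentation. SAP 8.1 pools events before and after rescue, and if rescue is more frequent in sham, an ocular study-eye excess from the UBX1325 injection may be attenuated. The direction follows from the sponsor's own assumed BCVA benefit; unequal rescue the other way would shift the difference the other way.

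The size is conditional. With 30% rescued in each arm it is under 1 point at 5–10% risk per injection. With 10% risk, 20% background and three injections per rescued patient, +8.0 becomes +3.0 at 50%/30% rescue and −1.1 at 60%/20%. With one injection per rescued patient the sign does not change in any scenario shown.

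Rescue is an intercurrent event after randomisation, so it should not be called baseline confounding. The sample size is untouched, and most systemic events are likely to be little affected. This is a cheap improvement to the tables and does not invalidate the primary summary.

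**What to change.** In SAP 8.1, keep the full 48-week by-arm tables as the main summary and add, by arm:
- ocular study-eye TEAEs, all and treatment-related, with onset before first rescue;
- the same with onset on or after first rescue, marking events that start on the day of first rescue, because the date alone does not show whether they came before or after the injection;
- the number of rescue injections and the length of pre-rescue follow-up.

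State that the 48-week tables describe events regardless of rescue and that the split tables are supplementary. Do not base the comparison on rates per patient-time for events that cluster at injection.

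The cost is some SAP wording and a few repeated tables. SAP 7.1 already needs rescue dates, and concomitant medications are recorded at each visit (Protocol 5.1.3). The rescue rules do not change. The downside is that the pre-rescue tables have shorter follow-up and informative censoring, since rescue follows CST or BCVA worsening. They must be read beside the full tables and must not replace them.
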